#### 7.1.3.4.2 Efficacy

The TED01RV study demonstrated that subjects with active moderate-to-severe TED experienced statistically significant and clinically meaningful results in the proportion of responders at Week 24 in the teprotumumab group relative to placebo (69% [29/42 subjects] versus 20% [9/43 subjects], respectively;  $p < 0.001$ ). Therapeutic effects were rapid, with responder rates in the teprotumumab group significantly greater than those in the placebo group at Weeks 6, 12, and 18 (all  $p < 0.001$ ). Specifically, the proptosis component of the responder analysis showed a mean (standard error) reduction of 2.46 mm (0.20) in the teprotumumab group compared to 0.15 mm (0.19) in the placebo group at Week 24 ( $p < 0.001$ ).

The secondary endpoints (QoL, proptosis, and CAS as continuous variables) supported the primary analysis conclusion that teprotumumab was superior to placebo in the treatment of this population.

[figure not shown]
In conclusion, for subjects with active ophthalmopathy, teprotumumab was more effective than placebo in reducing proptosis and the CAS.

#### 7.1.3.4.3 Pharmacokinetics

[REDACTED]

**Table 7.1 Single-Dose Pharmacokinetic Parameters (CHO Material)**

The image is a high-contrast, black and white abstract pattern. It features a grid of rectangles of varying sizes and orientations. A large, solid black rectangular block is positioned in the center-left area. To the right of this central block, there are several vertical columns of rectangles. Some of these columns are aligned horizontally, while others are offset. The pattern includes various line segments, such as a horizontal line near the top and several vertical lines that intersect the horizontal lines. The overall effect is a complex, geometric, and somewhat abstract design.

#### 7.1.3.4.4 Pharmacodynamic Markers

#### 7.1.3.4.5 Safety

##### 7.1.3.4.5.1 River Vision TED01RV Study

Treatment-emergent AEs (TEAEs) in TED01RV that were reported for at least 5% of the subjects in the teprotumumab group and had a greater frequency than that in the placebo group are shown in [Table 7.2](#). The majority of AEs were mild, required no treatment, and resolved while subjects remained on drug. Hyperglycemia, which was monitored by assessing blood glucose and HbA1c, was the only AE clearly identified as related to study drug.

**Table 7.2 Summary of TEAEs Reported in at Least 5% of Subjects in Teprotumumab Treatment Group and % is Greater Than Placebo**

TEAEs	Placebo N=44 n (%)	Teprotumumab N=43 n (%)	Summary Details for TEAEs in Teprotumumab Group
Any TEAE	32 (72.7)	32 (74.4)	
Nausea	4 (9.1)	8 (18.6)	Generally mild and reported after first/second infusions
Muscle spasms	2 (4.5)	8 (18.6)	Intermittent, 2/8 cases experienced for >1 week and treated with muscle relaxants
Diarrhea	2 (4.5)	6 (14.0)	Treatment required in 2/6 cases, 1 designated an SAE (see below)
Hyperglycemia	2 (4.5)	5 (11.6)	Mechanism-based AE
Alopecia	2 (4.5)	3 (7.0)	All mild and no treatment required
Dry skin	0	3 (7.0)	All mild, one case used topical dry skin cream
Dysgeusia	0	3 (7.0)	For 2/3 cases a transient “metallic” taste on Days 1-2
Headache	2 (4.5)	3 (7.0)	Generally mild, one subject took paracetamol
Paresthesia	0	3 (7.0)	“Tingling” reported in nose, feet or chest; variable onset and in 2/3 cases occurred on 1 day
Hearing impaired	0	3 (7.0)	Disparate symptoms, onset and duration (i.e., one unilateral with onset 16 weeks after end of therapy, one mild bilateral that resolved, one intermittent in a subject with positive history of tinnitus)
Weight loss	0	3 (7.0)	Variable timing; decreases range from 5-9 lb.

#### 7.1.3.4.5.2 Safety Data Oncology Studies

In the oncology program, over 700 subjects were treated with teprotumumab. The safety profile of teprotumumab in these studies was confounded by the poor health of the enrolled subjects (most had late-stage cancers) and the administration of combination therapy (teprotumumab in conjunction with other cytotoxic agents) in some subjects. Safety data from the oncology studies is summarized in the IB.

#### 7.1.3.4.5.3 Teprotumumab Material Safety Profile

[REDACTED]

[REDACTED]

[REDACTED]

[REDACTED]

#### 7.1.3.4.5.4 Sarcoma Monotherapy Study with Teprotumumab CHO Material

[REDACTED]

[REDACTED]

### 7.1.3.4.5.5 AEs of Special Interest

Following a comprehensive review of the safety data from the oncology studies and that from the TED01RV study, the following AESIs have been identified for the current study:

- Infusion reactions
- Hyperglycemia
- Muscle spasms
- Diarrhea

resolution of symptoms except in the case of subjects who experience an anaphylactic reaction; these subjects should be removed from the study.

In general, the decision to keep a subject on study treatment with teprotumumab should take into consideration potential risks and benefits to the subject. Prior to all future infusions of teprotumumab, these subjects should be pre-medicated with IV diphenhydramine 1 to 1.25 mg/kg (maximum: 50 mg), IV ranitidine 50 mg, IV dexamethasone 0.4 mg/kg (maximum: 20 mg), and/or acetaminophen 500 mg. In addition, all future infusions should be administered over approximately 90 minutes (but not less than 80 minutes). Vital signs should be taken every 15 minutes during the infusion.

Subjects who experience delayed-type hypersensitivity reactions (e.g., skin rash) may remain in the study at the discretion of the Investigator, and prior to all future infusions of teprotumumab, should be pre-medicated with the above medications (diphenhydramine, ranitidine, dexamethasone, and/or acetaminophen). Subjects who experience a worsening delayed-type hypersensitivity reaction following repeated infusions of teprotumumab or who have other signs of serum-sickness (e.g., delayed fever, myalgias, arthralgias) may be removed from the study after discussion with the Investigator and Sponsor.

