### **9.3.3 Removal of Subjects from Therapy or Assessment**

All subjects are free to withdraw from study participation at any time, for any reason, and without prejudice to their further medical care. In addition, the Investigator may terminate a subject from the study at any time. The primary reason for discontinuation from the study and/or study drug should be recorded on the eCRF using one of the following categories:

- Adverse Event. The subject experiences an AE that imposes an unacceptable risk to the subject's health, or the subject is unwilling to continue because of an AE. AEs requiring permanent study drug discontinuation per the protocol include:
  - A drug-related anaphylactic reaction.
  - A persistently severe drug-related AE that does not abate to mild or moderate intensity at least 2 weeks prior to the next scheduled dose.
  - Severe drug-related hyperglycemia (e.g., blood glucose > 250 mg/dL) that does not abate to mild or moderate intensity with anti-diabetic treatment (dose may be skipped up to 2 times prior to permanently discontinuing study drug; see [Section 9.4.6.3.2](#) for details).
  - Diagnosed or suspected IBD (e.g., diarrhea with or without blood or rectal bleeding associated with abdominal pain or cramping/colic, urgency, tenesmus, or incontinence for more than 4 weeks without a confirmed alternative diagnosis OR

endoscopic or radiologic evidence of enteritis/colitis without a confirmed alternative diagnosis).

- Lack of Efficacy. Removal of a subject from the study is at the discretion of the Investigator and may occur if the Investigator determines that study drug administration is not benefitting the subject and eye symptoms linked to progressing disease worsen posing an unacceptable risk to the subject. The specific care of the subject is best determined by the Investigator and managing physician(s) involved in the subject's care and may require removal from the study. All subjects are free to withdraw from study participation at any time, for any reason, allowing them to receive any specific treatment for TED that is considered necessary per their treating physician and local standard of care.
- Non-Compliance with Study Drug/Other/Protocol Deviations. The subject has a significant protocol deviation, does not comply with study drug administration schedule, or fails to adhere to other study requirements as stated in the protocol.

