## 9.4 Treatments

### 9.4.1 Treatments Administered

All study drug dosing will be performed at the clinic under the supervision of clinic staff. Subjects will receive 8 infusions of teprotumumab (10 mg/kg on Day 1 followed by 20 mg/kg q3W for the remaining infusions) in an open-label fashion.

The infusion rate may be reduced and the dose may be interrupted or held based on tolerability (see [Section 9.4.6.3.2](#) for details). The first and second infusions will be administered over approximately 90 minutes (but not less than 80 minutes). Subsequent infusions will be administered over approximately 60 minutes (but not less than 50 minutes), providing there are no significant infusion-associated events.

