#### **9.4.6.3.2 Dose Modifications, Interruptions, and Delays**

Subjects will be monitored for immediate infusion-associated events (e.g., nausea, vomiting, facial flushing, warmth, dyspnea, dizziness, hypertension, hypotension, pruritus) and delayed infusion-associated events (e.g., rash). If immediate infusion-associated events are noted, the infusion rate will be slowed or interrupted, symptomatic treatment (e.g., antipyretics, antihistamines, beta-agonists, oxygen, IV fluid) will be administered, and vital signs (temperature, blood pressure, pulse, and respiratory rate) will be monitored every 5 minutes until stable and then every 15 minutes for 2 additional determinations. The infusion may be restarted upon complete resolution of symptoms; however, study drug dosing will be permanently discontinued if the event is an anaphylactic reaction.

If delayed infusion-associated events are noted, subjects may continue dosing at the Investigator's discretion; however, if a rash worsens following repeated dosing or other signs of serum sickness (e.g., delayed fever, myalgias, arthralgias) are present, study drug dosing will be permanently discontinued.

Following the appearance of either immediate or delayed infusion-associated events, subsequent doses may be pre-treated with diphenhydramine (1 to 1.25 mg/kg IV; maximum of 50 mg), ranitidine (50 mg IV), famotidine (0.5 mg/kg IV), dexamethasone (0.4 mg/kg IV; maximum of 20 mg), and/or acetaminophen (500 mg). All subsequent infusions will be administered over approximately 90 minutes (but not less than 80 minutes) with vital signs monitored every 15 minutes from the start of the infusion through 60 minutes after infusion completion.

In general, the decision to continue dosing should take into consideration the potential benefit and risk to a subject.

Any severe drug-related AE must revert to mild or moderate in intensity at least 2 weeks prior to the next scheduled dose in order for the dose to be administered; if the AE remains severe in intensity within 2 weeks of the next scheduled dose, the subject will be withdrawn from treatment.

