### 9.5.4.1.3 Intensity of Adverse Events

All clinical AEs encountered during the clinical study will be reported on the AE form of the CRF. Intensity of AEs will be graded on a 5-point scale (mild, moderate, severe, life-threatening, death) and reported in detail on the eCRF.

Intensity	Definition	Corresponding NCI Grade
Mild	discomfort noticed but no disruption of normal daily activity	1
Moderate	discomfort sufficient to reduce or affect daily activity	2
Severe	inability to work or perform normal daily activity	3
Life-Threatening	represents an immediate threat to life	4
Fatal	results in death	5

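### Protocol Section 7.1.3.4.5.5.1 makes stopping optional for worsening delayed hypersensitivity or serum-sickness signs, while Section 9.4.6.3.2 makes it mandatory for nearly the same trigger

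*Protocol*

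**What the plan says.** Protocol Section 7.1.3.4.5.5.1 (precautions for adverse events of special interest, under Infusion-Associated Events) deals with delayed reactions in two steps. A subject with a delayed-type hypersensitivity reaction, for which skin rash is the example, "may remain in the study at the discretion of the Investigator, and prior to all future infusions of teprotumumab, should be pre-medicated". If that reaction worsens on repeated infusions, or other signs of serum sickness appear, the subject "may be removed from the study after discussion with the Investigator and Sponsor".

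Section 9.4.6.3.2 (Dose Modifications, Interruptions, and Delays) covers the same ground. Dosing may continue at the Investigator's discretion after a delayed event. But if a rash worsens on repeated dosing, or if "other signs of serum sickness (e.g., delayed fever, myalgias, arthralgias) are present, study drug dosing will be permanently discontinued".

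Section 9.3.3 lists adverse events that require permanent study drug discontinuation: drug-related anaphylaxis, a persistently severe drug-related event, severe drug-related hyperglycemia that does not abate, and diagnosed or suspected inflammatory bowel disease. Neither serum sickness nor a worsening delayed reaction is named, although the list is worded as open.

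The two sections also describe anaphylaxis differently. Section 7.1.3.4.5.5.1 removes the subject from the study, whereas Sections 9.3.3 and 9.4.6.3.2 require permanent discontinuation of study drug.

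**The concern.** A stopping rule should give one answer for one clinical picture. Here the examples of serum sickness are identical in the two sections, yet one section leaves the decision to discussion and the other has already made it. What is at stake is patient safety: a subject with early serum-sickness signs could be given another 20 mg/kg infusion by a site that believes it is following the protocol. Section 9.5.4.1.1.5 refers readers who want more on the events of special interest to Section 7.1.3.4.5.5, which is where the permissive sentence sits.

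The anaphylaxis wording raises a smaller matter. All sections end dosing, so re-exposure is not in question. Removing the subject from the study would, however, forgo the scheduled anti-drug antibody samples in Follow-Up, in subjects for whom immunogenicity data are especially relevant.

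**Working it through.** The plan states no figure to reproduce. The check compares the texts and then counts doses and samples.

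**1. Trigger and action side by side**

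| | Section 7.1.3.4.5.5.1 | Section 9.4.6.3.2 |
|---|---|---|
| First delayed reaction | May stay in the study; premedicate before future infusions | May continue dosing |
| Worsening on repetition | Any delayed-type hypersensitivity reaction | Rash |
| Serum-sickness signs | Delayed fever, myalgias, arthralgias | Same three |
| Action | *May* be removed, after discussion | Dosing *will* be permanently discontinued |
| Anaphylaxis | Removed from the study | Dosing permanently discontinued |

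The serum-sickness trigger is the same. The worsening trigger is slightly broader in Section 7. The actions differ: optional against mandatory.

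**2. Is the difference left over from an amendment?** No. The Version 3.0 summary of changes shows edits to both sections on the minimum infusion duration. Neither edit touches these sentences, and both stand in the current body.

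**3. Does the severe-event rule close the gap?** Section 9.4.6.3.2 says: "Any severe drug-related AE must revert to mild or moderate in intensity at least 2 weeks prior to the next scheduled dose". Section 9.3.3 matches it: "A persistently severe drug-related AE that does not abate to mild or moderate intensity at least 2 weeks prior to the next scheduled dose". On a three-weekly schedule the cut-off is 21 − 14 = day 7 after an infusion. This is nominal, because infusion visits have a ±3-day window. The rule therefore misses mild and moderate signs altogether, and severe signs that abate by about day 7. Section 9.5.4.1.3 defines moderate as "discomfort sufficient to reduce or affect daily activity", so what is missed need not be trivial.

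**4. Size of the gap in doses.** Eight infusions are planned: "10 mg/kg on Day 1 followed by 20 mg/kg q3W for the remaining infusions". After infusion k, 8 − k remain.
- Serum-sickness signs after infusion 1: 8 − 1 = 7
- Reaction that worsens at infusion 2 (the earliest repetition): 8 − 2 = 6
- Signs after infusion 7: 8 − 7 = 1
- Under Section 9.4.6.3.2, for every k: 0

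Every remaining infusion is at 20 mg/kg. Section 7 sets no limit, so 7 is a ceiling.

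**5. Antibody samples after anaphylaxis.** Sections 9.5.4.7 and 9.5.6.11 give these scheduled samples after early stopping: none at the Treatment Period premature-withdrawal visit, then Months 9 and 12 of Follow-Up. A lead-in non-responder who stays in Follow-Up gives 0 + 2 = 2; one removed from the study gives 0. Subjects who entered after relapse have no Follow-Up Period and give 0 either way.

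**The case against.** The strongest reply is that both sentences can be obeyed at once. Section 9.4.6.3.2 governs dosing and Section 7 governs study participation, and the protocol does separate the two: Section 9.3.3 records discontinuation from the study, from study drug, or from both. Read literally, the drug always stops and leaving the study is optional. The context weakens this reading. The sentence just before in Section 7 ties staying in the study to future infusions, and the matching sentence in Section 9.4.6.3.2 speaks of continued dosing. For anaphylaxis, too, Section 7 uses removal from the study where Section 9.4.6.3.2 stops the drug. The literal reconciliation is possible, but a site should not have to find it.

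The second reply is about hierarchy, and much of it stands. Section 7 is the Introduction. The Synopsis, Section 9.1 and Section 9.4.1 (for example, "The infusion rate may be reduced and the dose may be interrupted or held based on tolerability") all send the reader to Section 9.4.6.3.2, and Section 9.5.4.1.1.5 cites Section 7 only for further information. Stopping the drug breaches neither sentence, whereas re-infusing breaches Section 9.4.6.3.2. The Section 7 route also requires a discussion that involves the sponsor, and both sections ask for benefit and risk to be weighed. These safeguards make re-infusion less likely. They do not remove the conflict, because no clause states which section prevails.

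On anaphylaxis, the sample count covers scheduled samples only. Section 9.5.4.7 also has subjects with neutralizing antibodies followed until levels settle, and Section 9.3.3 continues follow-up of the event itself.

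**Conclusion.** The inconsistency is real, and worth correcting for patient safety at small cost. The protective rule already sits in the operative section and is the likelier one to be followed. The exposure is confined to a site that relies on the Section 7 precautions, and to signs that are mild, moderate, or severe but quickly abating. For such a subject the difference is 1 to 7 infusions. The readable text gives no rate for delayed reactions or serum sickness, so the number of subjects cannot be estimated; few are likely.

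Three stronger readings might be inferred, and the documents do not support them:
- **The protocol intends re-infusion after serum-sickness signs.** No sentence says so. It follows only from reading Section 7 alone.
- **Seven extra infusions is an expected exposure.** It is arithmetic on the schedule and assumes that every later safeguard fails.
- **The anaphylaxis wording allows re-exposure, or the conflict damages the primary endpoint.** Every section ends dosing after anaphylaxis. Stopping or continuing after a delayed reaction could change one subject's responder status under SAP Section 8.1, but nothing in the documents sizes that, and the point does not depend on it.

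The conclusion assumes that staying in the study, in the Section 7 paragraph, means continuing to receive infusions, as its wording and the parallel text in Section 9.4.6.3.2 indicate.

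**What to change.** Three linked edits are needed, because changing the Section 7 action alone would cite a rule that Section 9.4.6.3.2 does not fully contain.

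1. **Section 7.1.3.4.5.5.1:** replace optional removal after discussion with mandatory permanent discontinuation of study drug, with a reference to Section 9.4.6.3.2.
2. **Section 9.4.6.3.2:** widen the trigger from rash to a delayed-type hypersensitivity reaction (rash as the example) that worsens on repeated dosing, or other signs of serum sickness.
3. **Section 9.3.3:** add this trigger to the list of events requiring permanent study drug discontinuation.

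Minor companion edit: for anaphylaxis in Section 7.1.3.4.5.5.1, replace removal from the study with permanent study drug discontinuation and the Week 24/premature-withdrawal assessments. Lead-in non-responders would then be encouraged to continue in Follow-Up, as the Schedule of Assessments footnote already provides. This keeps their scheduled Month 9 and Month 12 antibody samples.

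The cost is a few sentences in three sections. The only substantive change is that the mandatory stop would also cover worsening delayed reactions other than rash, which the sponsor should confirm clinically. No visit, sample size or analysis changes.

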#### Hyperglycemia

In preclinical studies, there was no *in vitro* cross-reactivity of teprotumumab with the insulin receptor. During TED01RV, among non-diabetic subjects, hyperglycemia occurred at comparable rates in both treatment groups and was uniformly Grade 1 and intermittent. Among diabetic subjects, Grade 2 or 3 hyperglycemia occurred in some teprotumumab-treated subjects; this was well-controlled after diabetes medication adjustment. Glycemic control, as assessed by HbA1c, was at baseline levels following the treatment phase for all subjects in the teprotumumab group.

Subjects with known controlled diabetes mellitus are allowed to participate in studies with teprotumumab. HbA1c levels should be monitored regularly in these subjects. Investigators are strongly encouraged to adjust their subjects' diabetes management to maintain subjects' HbA1c levels at  $\leq 7\%$ . In the event a subject's HbA1c level rises to  $> 7\%$  while in the study, the Investigator must determine the risk versus benefit for each subject to remain in the study.

Fasting glucose levels (after at least an 8-hour fast) should be tested at Baseline. Hyperglycemia should be promptly investigated and managed. Subjects with recurrent hyperglycemia, defined as a fasting glucose level of moderate intensity (glucose  $> 160 - 250$  mg/dL), will require evaluation for diabetes mellitus (e.g., fasting glucose, glucose tolerance, and HbA1c tests) and appropriate medical management at the discretion of the Investigator.

#### Muscle Spasms

During the TED01RV study, muscle spasms were identified in 19% of the subjects receiving teprotumumab versus 5% of those receiving placebo. In the teprotumumab group, 8 subjects had muscle spasms (6 had Grade 1 and 2 had Grade 2); only 2 subjects experienced the event for longer than one week and were treated with muscle relaxants. If possible, avoid medications

known to cause muscle spasms or muscle toxicity such as diuretics or statins and evaluate for other causes of muscle spasm such as electrolyte abnormalities and dehydration.

## **7.2 Rationale for this Study**

Multiple lines of evidence indicate that IGF-1R plays a critical role in regulating the autoimmune response that underlies TED. Teprotumumab is a mAb with low nanomolar affinity for human IGF-1R. Binding of teprotumumab to IGF-1R blocks receptor activation by agonists, IGF1 and IGF2, and also causes direct inactivation of the receptor through antibody-induced internalization. Teprotumumab has no agonist activity for canonical IGF-1R signaling pathways and is highly selective; in particular, it does not recognize the insulin receptor. Teprotumumab is well-tolerated in humans at doses that produce > 90% IGF-1R occupancy. Systemic administration of teprotumumab to subjects with moderate-to-severe active TED should, therefore, attenuate all disease symptoms that are dependent on IGF-1R activation. This argument holds whether IGF-1R is being activated by GD-IgG or endogenous ligands IGF-1 and IGF2, or whether the receptor is expressed on fibroblasts, progenitor fibrocytes, adipocytes, or lymphocytes. Moreover, inhibition of IGF-1R receptor function with an antibody may also attenuate signaling through the TSHR, an autoantigen that has been implicated in TED, because IGF-1R and TSHR are physically and functionally coupled. Teprotumumab, therefore, has the potential to treat TED at multiple different molecular and cellular levels.

Administering teprotumumab early in active TED is designed to reduce the intensity and duration of the active disease, minimize the sequelae that are carried over to constitute inactive TED, and thereby have a beneficial effect on long-term outcome, reducing the need for corrective surgeries. Previous preclinical and clinical experience indicates that, at doses that are pharmacologically relevant for blocking IGF-1R, teprotumumab has an acceptable safety profile following IV infusion and is, therefore, a suitable drug candidate to be investigated in the TED indication.

Horizon is currently conducting a randomized, multicenter, double-masked, placebo-controlled study evaluating the efficacy and safety of teprotumumab in adult subjects with moderate to severe active TED (HZNP-TEP-301). This study (HZNP-TEP-302) is designed to be an open-label extension of HZNP-TEP-301, in which subjects who received 8 infusions of teprotumumab or placebo in HZNP-TEP-301 and were non-responders at the end of the Treatment Period or relapsed during the Follow-Up Period will be offered the opportunity to receive 8 infusions of teprotumumab.

